## **6 INVESTIGATORS AND STUDY PERSONNEL**

This study will be conducted by qualified investigators under the sponsorship of Eisai (the sponsor) at approximately 30 investigational sites in China.

The name and telephone and fax numbers of the medical monitor and other contact personnel at the sponsor and of the contract research organizations (CROs) are listed in the Investigator Study File provided to each site.

## 7 INTRODUCTION

### 7.1 Compound Overview

#### 7.1.1 Gout

Gout is caused by hyperuricemia which is defined as a serum uric acid (SUA) concentration greater than 7.0 mg/dL. At SUA levels greater than 7.0 mg/dL, uric acid crystals can precipitate out of solution and deposit in joints and other body tissues where they can produce an inflammatory response.

In China, there has been a continuing increase in gout patients in the recent years due to changing of dietary behavior, the prolongation of life span and the continuous improvement of health care. The prevalence of gout in China has been increasing rapidly during the past years (Multi-Disciplinary Expert Task Force on Hyperuricemia and Its Related Diseases, 2017). From meta analysis, the prevalence of gout is about 1.1% (Liu, et al., 2015). Gout has become the most common arthritis related to rheumatic disease of adult. Gout is generally thought as an independent risk factor for chronic kidney disease, hypertension, coronary heart disease (CHD), cardiovascular disease (CVD) and type 2 diabetes; and an independent predictor factor for premature death (Bardin and Richett, 2017). Gout stone can cause the joint deformity, gouty nephropathy, disability, even the death.

Management of hyperuricemia at an appropriate level is important for preventing acute gouty arthritis, gouty kidney, and urinary calculi. In addition, it may protect renal function, and reduce the risks of cardiovascular disorders (Siu, et al., 2006; Athyros, et al., 2004). Based on the findings above, it is thought that urate lowering treatment (ULT) will become much more important in the future.

#### 7.1.1.1 Current Treatment and Unmet Medical Needs

The etiology of hyperuricemia includes excessive production of uric acid, decreased excretion of uric acid, and the combined type. Approximately 90% of hyperuricemia is the uric acid decreased excretion type and the combined type in China (Chen, 2006).

The basic principle of selecting drug is based on classification of hyperuricemia. The xanthine oxidase inhibitor allopurinol has been used as a uric acid production inhibitor for many years; febuxostat is marketed later, and has been increasingly prescribed in recent years, but hepatic dysfunction, the incidence of cardiovascular death and all-cause mortality was reported to be high. Benzbromarone is the main uricosuric drug, but it can cause serious hepatic disorders (Van der Klauw, et al., 1994). It also has a potent inhibitory effect on the drug metabolizing enzyme cytochrome P450 (CYP), particularly on CYP2C9 (Kunishima, et al., 2003; Locuson, et al., 2003). So a potent, well-tolerated, and selective uricosuric drug without causing hepatic impairment, and less drug-drug interaction is needed in clinical practice.

### 7.1.2 Dotinurad

Fuji Yakuhin Co., Ltd. has conducted an intensive investigation on a novel uricosuric drug, and discovered dotinurad, which has a superior uricosuric effect derived from potent suppression of uric acid reabsorption.

Dotinurad reduces SUA levels by selectively inhibiting urate transporter 1 (URAT1), which is expressed on the proximal renal tubules and is responsible for reabsorption of uric acid.

## 7.2 Clinical Experience

The efficacy and safety of dotinurad were demonstrated in nonclinical studies and clinical studies. A total of 17 clinical studies for dotinurad were conducted in Japan, and dotinurad was approved for hyperuricemia and gout in Japan in January 2020. As for details on the results of these clinical studies for dotinurad, refer to the Investigator's Brochure.

## 7.3 Study Rationale

### 7.3.1 Targeting Population

For every gout patient, ULT should be considered and discussed. Appropriate ULT reduces the frequency of gout flare and avoids their reoccurrence. In addition, effective ULT reduces the size and number of tophi, therefor improving the quality of life of patients with gout. And it may protect renal function, and reduce the risks of cardiovascular disorders. So, ULT is recommended by the guidelines of ACR (American College of Rheumatology), EULAR (European League Against Rheumatology) and CRA (Chinese Rheumatology Association). Gout patients with SUA  $>7$  mg/dL and a history of gout attack or concurrent gout tophi will be enrolled.

### 7.3.2 Primary Endpoint

The target SUA level of  $\leq 6$  mg/dL is appropriate for the most of gout patients from the guideline. It is believed that SUA level  $\leq 6$  mg/dL allows dissolution of the crystals of urate, and maintain  $\leq 6$  mg/dL also can avoid new formation of urate crystals. European Medicines Agency (EMA) paper on guideline on clinical investigation of medicinal products for the treatment of gout (EMA/CHMP/774470/2018) suggests: for confirmatory trials, the primary endpoint should be defined as sustained SUA levels below a target level of 6 mg/dL, for a period of 3 consecutive months, which starts once the treatment is optimized and stable. And guideline for the diagnosis and management of hyperuricemia and gout in China (2019) also suggests to modify the dose based on patient's SUA level for achieving the target of SUA  $\leq 6$  mg/dL (Chinese Society of Endocrinology, Chinese Medical Association, 2020). Therefore, the proportion of subjects achieving a SUA level  $\leq 6.0$  mg/dL was selected for primary endpoint.

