### 7.3.3 Study Duration

Treatment I Phase of 4 weeks is selected to prevent the risk of gouty arthritis caused by a rapid decrease in the SUA level. The duration is based on Japan Phase 3 studies.

Eight-week duration of dotinurad 2 mg/day in Treatment II Phase is based on FYU-981-014 study, which was a Phase 3 study conducted in Japan. In FYU-981-014 study, the duration of 2 mg/day was 8 weeks. And it is sufficiently long for this duration to assess non-inferiority of dotinurad 2 mg and febuxostat 40 mg in Chinese patients. That allows us to compare Chinese data and Japanese data as necessary.

Twelve-week duration of dotinurad 4 mg/day in Treatment II Phase is based on EMA paper on guideline on clinical investigation of medicinal products for the treatment of gout (EMA/CHMP/774470/2018). According to this guideline, the pivotal trials should be sufficiently long to establish a sustained effect of urate lowering for at least 3 months, once the treatment is optimized at a stable dose level. So in this study, 12 weeks of dotinurad 4 mg/day is established.

EMA paper on guideline on clinical investigation of medicinal products for the treatment of gout also suggests that a parallel, randomized, double-blind trial should be performed for a minimum of 6 months. Therefore, subjects in the dotinurad group will be treated for 24 weeks in total.

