## **8 STUDY OBJECTIVES**

### **8.1 Primary Objective**

The primary objective of the study is to confirm the superiority of dotinurad 4 mg to febuxostat 40 mg on the proportion of subjects achieving a SUA level  $\leq 6.0$  mg/dL at Week 24 in Chinese subjects with gout.

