### **8.2 Secondary Objectives**

The secondary objectives of the study are:

- To confirm the non-inferiority of dotinurad 2 mg to febuxostat 40 mg on the proportion of subjects achieving a SUA level  $\leq 6.0$  mg/dL at Week 12 in Chinese subjects with gout
- To compare the proportion of subjects achieving a SUA level  $\leq 6.0$  mg/dL at each time point between treatment groups
- To compare the percent reduction in SUA level from baseline at each time point between treatment groups
- To compare the change in SUA level from baseline at each time point between treatment groups
- To compare the SUA level at each time point between treatment groups
- To evaluate the safety and tolerability of dotinurad

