### 9.7.1.1 Study Endpoints

#### 9.7.1.1.1 PRIMARY ENDPOINT

The primary endpoint is the proportion of subjects with  $\leq 6.0$  mg/dL in SUA level at Week 24 (LOCF).

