#### 4.4.2 Secondary Efficacy Analyses

For all the secondary efficacy analyses, no multiplicity adjustment will be made.

- Proportion of subjects with  $\leq 6.0$  mg/dL in SUA level at Week 12 (LOCF)

The difference in responder rate at Week 12 (LOCF) between dotinurad 2 mg and febuxostat 40 mg and the stratified 95% confidence interval will be estimated based on Mantel–Haenszel method adjusting for the baseline SUA level and baseline BMI. The prespecified non-inferiority margin will be  $-10\%$  in this analysis, which will be for the reference purpose only. The number (percentage) of responder and the asymptotic 95% confidence interval at Week 12 (LOCF) (see section 7) will be presented by treatment group.

The same analysis mentioned above will be repeated supplementally based on the PP Analysis Set.

- Proportion of subjects with  $\leq 6.0$  mg/dL in SUA level at each time point

The number (percentage) of responder at each visit (Week 4, Week 8, Week 12, Week 16, Week 20, Week 24) will be presented by treatment group.

Responder rate for each treatment group at each visit (Week 4, Week 8, Week 12, Week 12 (LOCF), Week 16, Week 20, Week 24, Week 24 (LOCF)) will be presented by bar chart.

- Mean percent reduction from baseline in SUA level at each time point

The mean percent reduction from baseline in SUA level at each visit (Week 4, Week 8, Week 12, Week 12 (LOCF), Week 16, Week 20, Week 24, Week 24 (LOCF)) will be summarized by treatment group using descriptive summary statistics. In addition, box-plot will be used for graphical presentation.

The following subgroup analysis will be repeated:

- SUA level category ( $<9$ ; 9 to  $<10$ ; 10 to  $<11$ ;  $\geq 11$  mg/dL)
- BMI category ( $<25$ ;  $\geq 25$  kg/m $^2$ )
- Classification of hyperuricemia (overproduction type, underexcretion type, combined type, other type)

In addition, the mean percent reduction and difference in least squares (LS) means between dotinurad and febuxostat, and corresponding 95% confidence interval will be estimated based

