on the mixed-effects models for repeated measures (MMRM). The model will be adjusted for the baseline SUA value, baseline SUA level category (<9; 9 to <10; 10 to <11;  $\geq 11$  mg/dL) and baseline BMI category (<25;  $\geq 25$  kg/m^2), treatment, time (Week 4, Week 8, Week 12, Week 16, Week 20, Week 24) and the interaction of treatment by time. The Kenward-Roger approximation will be used to estimate denominator degrees of freedom. The unstructured covariance matrix (UN) will be used in the analysis. In the case of nonconvergence of UN, the toeplitz covariance matrix (TOEP) will be used. In the case of nonconvergence with TOEP, the autoregressive covariance matrix [AR (1)] will be used in the model. The use of MMRM will be based on the assumption of missing at random (MAR), which means no imputation for missing values will be conducted.

- Mean SUA level and mean change from baseline in SUA level at each time point

The mean actual value and the mean change from baseline in SUA level at each time point (Baseline, Week 4, Week 8, Week 12, Week 16, Week 20, Week 24, Week 24 (LOCF)) will be summarized by treatment group using descriptive summary statistics and presented by box-plot.

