#### 4.4.3 Other Efficacy Analyses

No other efficacy analyses are planned for this study.

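### Does the plan need a count of the subjects who stay at target throughout the 4 mg period?

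*Protocol*

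**What the plan says.** Protocol 7.3.2 gives the reasons for the primary endpoint. It reports the EMA gout guideline as suggesting that "the primary endpoint should be defined as sustained SUA levels below a target level of 6 mg/dL, for a period of 3 consecutive months", counted from the point at which treatment is optimized and stable. It also cites a Chinese guideline on adjusting the dose to reach the target. It then selects the proportion of subjects at or below 6.0 mg/dL.

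Protocol 7.3.3 uses the EMA guideline for a different purpose, the length of treatment: "the pivotal trials should be sufficiently long to establish a sustained effect of urate lowering for at least 3 months". From this it sets 12 weeks on dotinurad 4 mg.

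The primary objective (Protocol 8.1) is superiority on the proportion at target "at Week 24 in Chinese subjects with gout". Protocol 9.7.1.1.1 and SAP 4.1.1 define the endpoint at Week 24 with LOCF. Apart from Week 12 non-inferiority and safety, the secondary objectives (Protocol 8.2) are set visit by visit, for example "To compare the percent reduction in SUA level from baseline at each time point between treatment groups".

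SAP 4.4.2 follows that structure: "The number (percentage) of responder at each visit (Week 4, Week 8, Week 12, Week 16, Week 20, Week 24) will be presented" for each arm. An MMRM on percent reduction has terms for treatment, time "and the interaction of treatment by time". SAP 4.4.3 then closes the list: "No other efficacy analyses are planned for this study".

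**The concern.** A reader of Protocol 7.3.2 expects an endpoint about holding the target for three months and finds one about a single visit. The obvious follow-up question is how many subjects stayed at target on the final dose. The planned tables cannot answer it. Visit-wise percentages are margins, and different subjects may be at target at Weeks 16, 20 and 24. The MMRM describes mean percent reduction, not who is at target.

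The samples are already scheduled, so the omission looks avoidable. If the count were first made after unblinding, it could only be a labelled exploratory analysis under SAP 4.8. At stake would be a mismatch between the reasons given for the endpoint and what the trial can show about durability of response.

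**Working it through.** **1. Do objectives, endpoints and analyses match?**

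| Objective (Protocol 8.1, 8.2) | Endpoint (Protocol 9.7.1.1, SAP 4.1) | Analysis (SAP 4.4.1, 4.4.2) |
|---|---|---|
| Superiority at Week 24 | Proportion at target, Week 24 (LOCF) | Stratified CMH test, Mantel–Haenszel difference with 95% CI; non-responder imputation; PP repeat |
| Non-inferiority at Week 12 | Proportion at target, Week 12 (LOCF) | Mantel–Haenszel difference with 95% CI, margin −10% for reference |
| Proportion at target, each time point | Same | Number and percentage by visit |
| Percent reduction, each time point | Same | Descriptive statistics and MMRM |
| Change and level, each time point | Same | Descriptive statistics |

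Every efficacy objective has an endpoint and an analysis. None concerns the same subject being at target at several visits.

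**2. Is the duration argument in 7.3.3 carried out?** Protocol Table 1 gives 4 mg from Day 85 to Day 168: 168 − 85 + 1 = 84 days, or 12 weeks. SUA samples at Days 112, 140 and 168 fall inside that period. The cited sentence asks for a trial long enough to establish a sustained effect. Responder rates at Weeks 16, 20 and 24, and MMRM contrasts at the same visits, show whether the group effect holds over those weeks.

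**3. Is the sample size affected?** Inputs from Protocol 9.7.2: 45% and 60%, 225 per group, two-sided 0.05. Pooled rate: (0.45 + 0.60)/2 = 0.525.

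- SE under the null: √(2 × 0.525 × 0.475 / 225) = 0.0471
- SE under the alternative: √((0.45 × 0.55 + 0.60 × 0.40) / 225) = 0.0465
- Power: Φ((0.15 − 1.96 × 0.0471) / 0.0465) = Φ(1.24) = 0.893

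The stated figure of about 90% is reproduced. It concerns Week 24 alone and does not depend on Weeks 16 or 20.

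**4. What would an all-visits count look like?** The documents give no Week 16 or Week 20 rate and no between-visit correlation, so this is an illustration. Assume 60% and 45% at all three visits, an exchangeable latent normal variable with correlation ρ equal in both arms, and no missing visits. With t = Φ⁻¹(p), the share at target at all three visits is the integral over u of Φ((t − √ρ·u)/√(1 − ρ))³ φ(u).

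| ρ | Dotinurad | Febuxostat | Difference (from unrounded rates) |
|---|---|---|---|
| 0 | 21.6% | 9.1% | 12.5 points |
| 0.5 | 35.0% | 20.7% | 14.4 points |
| 0.7 | 41.2% | 26.4% | 14.8 points |
| 0.9 | 49.4% | 34.4% | 15.0 points |
| 1 | 60% | 45% | 15 points |

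At ρ = 0.5 the 95% CI half-width is 1.96 × √((0.350 × 0.650 + 0.207 × 0.793)/225) = 8.2 points. At 0.7 and 0.9 it is 8.6 and 9.0 points. For ρ from 0.5 to 0.9 the level falls by 10.6 to 25.0 points (60 − 49.4 and 60 − 35.0 for dotinurad; 10.6 to 24.3 for febuxostat). The difference between arms hardly moves.

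**5. Would the count deliver the cited three months?** Only in part. The three samples span 168 − 112 = 56 days of the 84. At Week 16 the dotinurad arm has had 112 − 85 + 1 = 28 days on 4 mg, and the febuxostat arm 112 − 29 + 1 = 84 days on 40 mg. The cited target is below 6 mg/dL, while the endpoint counts values at or below 6.0.

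**The case for a change.** The strongest case is that 7.3.2 is about how the endpoint should be defined, not only about trial length. For a responder endpoint, sustained naturally means the same subject at each visit. The margins do not settle that. In the illustration, one and the same visit-wise table is compatible with all-visits rates from 21.6% to 60% on dotinurad and from 9.1% to 45% on febuxostat. The near-constant difference also relies on equal correlation in the two arms. With 0.5 on dotinurad and 0.9 on febuxostat it would be 35.0 − 34.4 = 0.6 points; with the reverse, 49.4 − 20.7 = 28.7 points. The extra table would need no new sample.

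The factual part stands: the planned outputs cannot give the share of subjects at target throughout. The step from there to a defect does not. Section 7.3.2 reports a suggestion and then states its own choice; it never says that the chosen endpoint measures sustained response. The documents do not define sustained as every scheduled visit per subject, so that reading has to be supplied from outside them. The count would also need rules that the documents do not give for this purpose, such as how to treat unusable samples and subjects taken off treatment. SAP 2 and 4.8 leave room for a labelled additional analysis should the question arise.

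**Conclusion.** The concern does not hold. Followed as written, the plan answers each stated efficacy objective with a matching endpoint and analysis. The primary test, its power (0.893 against about 90% stated) and its type I error are unaffected. The duration argument in Protocol 7.3.3 is met by 84 days on 4 mg with three SUA samples and visit-wise group results. No number, rule or estimate in the plan needs correcting.

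What remains is an optional supportive table. It would describe 56 of the 84 days and, on the assumptions in step 4, show lower percentages with a difference of 14.4–15.0 points for correlations of 0.5 to 0.9. Those figures depend on equal visit rates, equal correlation in both arms and complete data, none of which the documents supply. The conclusion does not rest on them. It rests on the agreement between objectives, endpoints and analyses, and on the fact that 7.3.2 makes no commitment to a per-subject sustained response.

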### 7.3.3 Study Duration

Treatment I Phase of 4 weeks is selected to prevent the risk of gouty arthritis caused by a rapid decrease in the SUA level. The duration is based on Japan Phase 3 studies.

Eight-week duration of dotinurad 2 mg/day in Treatment II Phase is based on FYU-981-014 study, which was a Phase 3 study conducted in Japan. In FYU-981-014 study, the duration of 2 mg/day was 8 weeks. And it is sufficiently long for this duration to assess non-inferiority of dotinurad 2 mg and febuxostat 40 mg in Chinese patients. That allows us to compare Chinese data and Japanese data as necessary.

Twelve-week duration of dotinurad 4 mg/day in Treatment II Phase is based on EMA paper on guideline on clinical investigation of medicinal products for the treatment of gout (EMA/CHMP/774470/2018). According to this guideline, the pivotal trials should be sufficiently long to establish a sustained effect of urate lowering for at least 3 months, once the treatment is optimized at a stable dose level. So in this study, 12 weeks of dotinurad 4 mg/day is established.

EMA paper on guideline on clinical investigation of medicinal products for the treatment of gout also suggests that a parallel, randomized, double-blind trial should be performed for a minimum of 6 months. Therefore, subjects in the dotinurad group will be treated for 24 weeks in total.

### 7.3.4 Dose of Dotinurad

All antihyperuricemia drugs should be started from the low dose to avoid gout attack. Even though the approved starting dose of dotinurad in Japan is 0.5 mg/day, Chinese key opinion leaders (KOLs) suggested that 0.5 mg/day is low in terms of efficacy of dotinurad and half of treatment dose (2 mg/day), ie, 1 mg/day would be appropriate for starting dose of dotinurad. Study FYU-981-014 showed that 20-mg febuxostat group had a similar reduction rate in SUA levels ( $33.39\pm9.26\%$ ) to 1-mg dotinurad group ( $30.53\pm10.16\%$ ). This result suggests that the risk of acute gout attack caused by a rapid decrease in the SUA levels with 1 mg/day dotinurad is less likely to be exceeded 20 mg/day febuxostat. The above points suggest that the incidence of gout attack at 1 mg/day is acceptable in clinical practice.

The proportion of subjects achieving SUA level  $\leq6.0$  mg/dL at the final visit was 84.8% (84/99 subjects) and 88.0% (88/100 subjects) in the 2-mg dotinurad group and 40-mg febuxostat group, respectively in Study FYU-981-014. From the Chinese Phase 3 studies of febuxostat, the proportion of subjects achieving SUA level  $\leq6.0$  mg/dL tends to be approximately lower than that of Japanese subjects with the same dose of drug, is around 45%. Even though the responder rate with dotinurad 2 mg/day was over 80% in Japanese subjects, 4 mg/day might be needed to achieve SUA level  $\leq6.0$  mg/dL in Chinese subjects.

The above points suggest it is appropriate that the titration of 1 mg/day (for 4 weeks) to 2 mg/day (for 8 weeks) of dotinurad; and increase dose to 4 mg/day (for 12 weeks).

### 7.3.5 Choice of Comparator Drug

Dotinurad and benzbromarone have the same mode of action (MOA), both belong to uricosuric drugs. However, benzbromarone is launched decades ago, and febuxostat has been increasingly prescribed in recent years, and is taking the place of benzbromarone's share in China. Considering these, comparison data with febuxostat will be more useful for the clinical positioning of dotinurad after launched.

#### **Dose of Febuxostat**

All ULTs should be started at a low dose and then titrated upwards, to avoid and decrease the acute gout attack. “Guideline for the diagnosis and management of hyperuricemia and gout in China (2019)” recommends to start from 20 mg/day for febuxostat (Chinese Society of Endocrinology, Chinese Medical Association, 2020), and “Chinese multi-disciplinary consensus on the diagnosis and treatment of hyperuricemia and its related diseases” recommends the starting dose of 20 to 40 mg/day (Multi-Disciplinary Expert Task Force on Hyperuricemia and Its Related Diseases, 2017). Given the above, febuxostat 20 mg was selected as a starting dose.

In Phase 3 studies of febuxostat in China (CTR20150590, CTR20130132 and CTR20130048), febuxostat 40 mg was selected to assess non-inferiority compared allopurinol 300 mg, which is set as a daily dose in its package insert. One of those Phase 3 studies selected only one dose strength, febuxostat 40 mg. Considering above, febuxostat 40 mg was selected as a compared dose.

